The randomization to treatment groups is stratified by age (adolescent participants 12 to <18 years versus adults ≥ 18 years) and baseline disease severity (IGA 3 versus 4). Unless otherwise specified, the statistical analysis models for the Induction Period will adjust for age and baseline disease severity.

For assessments of the primary endpoints and other binary efficacy and health outcome endpoints, the following will be provided:

- Crude proportions for each treatment group along with the 95% two-sided asymptotic (that is, not continuity corrected) confidence intervals (CIs).
- The estimated common risk difference along with 95% CIs: The common risk difference is the difference in proportions adjusted for the stratification factors. SAS® PROC FREQ will be used for the estimates and CIs, where the CIs are calculated by using Mantel-Haenszel-Sato method (Sato 1989).
- Cochran-Mantel-Haenszel (CMH) test will be used to compare the treatment groups while adjusting for the stratification factors. The CMH p-value will be reported, and the CMH adjusted odds ratio (OR) along with the 95% two-sided asymptotic (that is, not continuity corrected) CIs.

Treatment comparisons of key continuous efficacy variables and health outcome variables at each post-baseline time point will be made using analysis of covariance (ANCOVA) with the following in the model: treatment group, baseline value, and stratification factors. Type III tests for least squares (LS) means will be used for statistical comparison between treatment groups. The LS mean difference, standard error (SE), p-value, and 95% CI, unless otherwise specified, will also be reported.

Treatment comparisons of other continuous efficacy variables and health outcome variables with multiple post-baseline measurements will be made using mixed-model for repeated measures (MMRM). When MMRM is used, the model includes treatment, baseline value, visit, the interaction of the baseline value-by-visit, the interaction of treatment-by-visit, and the stratification factors as fixed effects. The covariance structure to model the within-participant

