4.9. Changes to Protocol-Planned Analyses

- Removed analysis for other secondary endpoint of “Number of Skin Pain-Free (Skin Pain NRS = 0) days”
- Updated definition of analysis population for the Maintenance Period

5. Sample Size Determination

Approximately 280 participants will be randomized at a 3:2:2 ratio to lebrikizumab 250 mg Q2W, lebrikizumab 250 mg Q4W, or placebo (120 participants: 80 participants: 80 participants). The inclusion of approximately 15 adolescents is based on enrollment feasibility in Japan.

The assumed IGA score of 0 or 1 at Week 16 response rates are 38% for lebrikizumab 250 mg Q2W, 33% for lebrikizumab 250 mg Q4W, and 13% for placebo. The assumed EASI-75 response rates at Week 16 are 58% for lebrikizumab 250 mg Q2W, 53% for lebrikizumab 250 mg Q4W, and 20% for placebo. The assumptions for lebrikizumab are based on the DRM06-AD01 Phase 2b study, and the proportion of participants who achieved an IGA score of 0 or 1 and proportion of participants who achieved EASI-75 response at Week 16 using the rescue medication non-response sensitivity analysis, adjusting for the allowed use of TCS. The placebo response rate is based on the review of historical TCS clinical studies in AD (Simpson et al. 2016). This study has >95% and >80% power to test the superiority of lebrikizumab 250 mg Q2W to placebo and lebrikizumab 250 mg Q4W to placebo in the co-primary endpoints based on a two-sided Fisher exact test with alpha of 0.05.

6. Supporting Documentation

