		N/A	Descriptive statistics	Maintenance W16 Escape Population	No comparisons. All scheduled visits in the Maintenance Period	Secondary analysis
	Change from baseline in Itch NRS daily score for Day 1 through Day 15	Supportive Estimand (Hypothetical)	MMRM	ITT	Leb 250 mg Q2W vs PBO; Leb 250 mg Q4W vs PBO; Day 1 through Day 15 in the Induction Period	Secondary analysis
	Percentage change from baseline in Itch NRS daily score for Day 1 through Day 15	Supportive Estimand (Hypothetical)	MMRM	ITT	Leb 250 mg Q2W vs PBO; Leb 250 mg Q4W vs PBO; Day 1 through Day 15 in the Induction Period	Secondary analysis
	Proportion of participants achieving at least 4-point improvement in Itch NRS prorated weekly mean score in participants who had baseline Itch NRS ≥ 4	Primary Estimand (Hybrid)	CMH analysis with MCMC-MI	ITT with baseline Itch NRS ≥ 4	Leb 250 mg Q2W vs PBO; Leb 250 mg Q4W vs PBO; Week 16 and all scheduled visits in the Induction Period	Key secondary analysis: Weeks 1, 2, 4, and 16; Secondary analysis: other timepoints
		Supportive Estimand (Composite)	CMH analysis with tipping point analysis	ITT with baseline itch NRS ≥ 4	Leb 250 mg Q2W vs PBO; Leb 250 mg Q4W vs PBO; Weeks 1, 2, 4 and 16	Sensitivity analysis
		Supportive Estimand (Composite)	CMH analysis with NRI	ITT with baseline Itch NRS ≥ 4	Leb 250 mg Q2W vs PBO; Leb 250 mg Q4W vs PBO; Week 16 and all scheduled visits in the Induction Period	Supplementary analysis

Measure	Variable	Estimand (Section 1.1.1)	Analysis Method (Section 4.1)	Population (Section 3)	Comparison/Time Point	Analysis Type
	Proportion of participants achieving at least 4-point improvement in Itch NRS daily score in participants who had baseline Itch NRS ≥ 4 for Day 1 through Day 15	Supportive Estimand (Composite)	CMH analysis with NRI	ITT with baseline Itch NRS ≥ 4	Leb 250 mg Q2W vs PBO; Leb 250 mg Q4W vs PBO; Day 1 through Day 15	Secondary analysis
	Proportion of participants maintaining ≥ 4 -point reduction from baseline among those participants with Itch NRS of ≥ 4 -point at baseline who achieved ≥ 4 -point reduction from baseline at Week 16	Maintenance Primary Estimand (Hybrid)	Descriptive statistics with MCMC-MI	MPP with Itch NRS of ≥ 4 -points at baseline and who achieved ≥ 4 -point reduction from baseline at Week 16	No comparisons. All scheduled visits in the Maintenance Period	Secondary analysis
		Maintenance Supportive Estimand (Hybrid)	Descriptive statistics with MCMC-MI			Supplementary analysis

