Infliximab, Infliximabum, Etanercept, Etanerceptum, Adalimumab, Adalimumabum, Certolizumab, Certolizumabum, Certolizumab pegol, Golimumab, Golimumabum, Ozoralizumab, Afelimumab, Afelimumabum, Tumor Necrosis Factor Alpha (TNF-) Inhibitors, Tabalumab, Tregalizumab, Anakinra, Basiliximab, Basiliximabum, Daclizumab, Daclizumabum, Tocilizumab, Tocilizumabum, Mepolizumab, Mepolizumabum, Rilonacept, Rilonaceptum, Ustekinumab, Canakinumab, Briakinumab, Fezakinumab, Sirukumab, Sarilumab, Lebrikizumab, Secukinumab, Olokizumab, Gevokizumab, Brodalumab, Ladarixin, Ixekizumab, Dupilumab, Tildrakizumab, Tildrakizumabum, Reslizumab, Reslizumabum, Guselkumab, Guselkumabum, Olamkicept, Fletikumab, Bimekizumab, Mirikizumab, Risankizumab, Abatacept, Ligelizumab, Vedolizumab, Belimumab, Nemolizumab, Tralokinumab, Omalizumab

Phototherapy or Photochemotherapy:

Programming search of medication name (actual term or preferred term) contains ‘photo’ or ‘UV’ then medicals to manually review to confirm whether the medication in question is indeed ‘Phototherapy’ or ‘Photochemotherapy’

6.14. Appendix 14: Details of Combining Estimates and Test Statistics for Categorical Endpoints with Multiple Imputation

Following the implementation of MCMC-MI imputation as specified in Section 4.1.6.1.1, the 25 data sets with imputations should be set together and sorted by imputation number. The following sections describe the processes for combining inferences for the individual imputed data sets into one inference for reporting. All calculations are performed in SAS software version 9.4.

Summarize Unadjusted Response Rate

The response rates, overall and by treatment arm, and their associated SEs are computed for each imputed data set using PROC FREQ with the *riskdiff* option specified for the appropriate column in the TABLES statement. The response rates and SEs from the resulting output are combined across the 25 imputed data sets using PROC MIANALYZE, separately for each arm and the overall group.

Note that the estimate and 95% CI bounds output by PROC MIANALYZE are percents (i.e., they are in terms of the response rate). To obtain the number of responders, the estimated percent is multiplied by the number of individuals in the analysis population and rounded to the nearest integer.

Compute Stratified Measures of Association

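### Per-arm response rates in the Induction Period get an uncorrected Wald 95% interval with no low-count fallback, so it collapses or undercovers where responders are few

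*SAP*

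**What the plan says.** SAP Section 4.1.1 introduces its outputs with "For assessments of the primary endpoints and other binary efficacy and health outcome endpoints, the following will be provided". The first is "Crude proportions for each treatment group along with the 95% two-sided asymptotic (that is, not continuity corrected) confidence intervals (CIs"). The treatment effect has a separate interval, the stratified risk difference, "where the CIs are calculated by using Mantel-Haenszel-Sato method", together with the CMH test and adjusted odds ratio.

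SAP Appendix 14 explains how per-arm rates are handled after imputation: PROC FREQ yields a rate and standard error for each data set, and "The response rates and SEs from the resulting output are combined across the 25 imputed data sets using PROC MIANALYZE". No score or exact interval is named in either place, and there is no alternative for zero or very low counts.

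SAP Appendix 2 applies this to all Induction visits for several demanding endpoints. IGA 0 and SCORAD90 use NRI, as does the daily 4-point Itch response on Days 1 to 15. EASI-90 and the weekly Itch response use MCMC-MI as the main method. For weekly Itch the table marks "Key secondary analysis: Weeks 1, 2, 4, and 16", so the earliest time points carry major secondary status.

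**The concern.** The Wald standard error is estimated from the observed rate. It shrinks towards zero as the count falls and equals zero when nobody responds. The interval is then narrowest where the data say least. A placebo rate of 0% printed with limits (0, 0) claims certainty that 80 participants cannot give, and a negative lower limit is impossible for a proportion.

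One rule serves every Induction visit, so the problem would appear in the early and stringent-response rows of the tables. What is at stake is the honesty of error bars labelled 95%. No test result depends on them.

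**Working it through.** **Inputs.** SAP Section 5 gives the allocation to Q2W, Q4W "or placebo (120 participants: 80 participants: 80 participants"). It assumes Week 16 IGA 0/1 rates of "38% for lebrikizumab 250 mg Q2W, 33% for lebrikizumab 250 mg Q4W, and 13% for placebo" and EASI-75 rates of "58% for lebrikizumab 250 mg Q2W, 53% for lebrikizumab 250 mg Q4W, and 20% for placebo". The documents give no rates for Weeks 1 to 4, so 0.5% to 10% is an assumed range.

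**The plan's own figure.** No coverage is stated. The only figures built on these inputs are the powers, >95% (Q2W) and >80% (Q4W). Exact enumeration of the two-sided Fisher test gives 98.0% (IGA) and >99.9% (EASI-75) for Q2W, and 82.5% and 99.1% for Q4W. Joint power is therefore at least 0.9795 + 0.9998 − 1 = 97.9% and 0.8254 + 0.9906 − 1 = 81.6%. The stated figures reproduce.

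**Formulas.** Wald: p ± 1.96 × √(p(1 − p)/n). Exact coverage at true rate π is the sum of the binomial probabilities P(X = x) over every x whose interval contains π. P(0 responders) = (1 − π)^n. These are complete-data calculations.

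**Planned Week 16 rates.** Wald coverage is 94.4% (n = 80, 13%), 93.2% (80, 20%), 95.2% (120, 38%), 95.6% (80, 33%), 94.7% (120, 58%) and 94.3% (80, 53%).

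**Low rates, n = 80 (rates assumed).**

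| True rate | P(0 responders) | Wald coverage | Wilson coverage |
|---|---|---|---|
| 0.5% | 67.0% | 33.0% | 93.9% |
| 1% | 44.8% | 55.2% | 95.3% |
| 2% | 19.9% | 80.0% | 97.8% |
| 3% | 8.7% | 91.0% | 96.7% |
| 5% | 1.7% | 90.7% | 93.7% |
| 8% | 0.1% | 88.0% | 96.5% |
| 10% | <0.1% | 90.0% | 96.3% |

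Up to 2% the shortfall is almost entirely the chance of a (0, 0) interval: 1 − 0.448 = 0.552 and 1 − 0.199 = 0.801.

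**Other sizes.** With n = 120, Wald coverage is 70% at 1%, 91% at 2% and 88–95% from 3% to 10%. The Itch response analyses include only participants with a baseline score of at least 4, so those arms can be smaller. At an assumed n = 70, coverage is 50% at 1%, 75% at 2% and 86% at 5%.

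**Single results.** For 0/80, Wald gives (0, 0) and Wilson gives 0 to 3.84/(80 + 3.84) = 4.6%. For 1/80, Wald gives 0.0125 ± 1.96 × √(0.0125 × 0.9875/80) = −1.2% to 3.7%, and Wilson gives 0.2% to 6.7%.

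**Under MI.** The pooled variance is T = W + (1 + 1/25)B, where W is the mean within-imputation variance and B the between-imputation variance. If no data set has a responder, W = B = T = 0. If one of the 25 has a single responder in 80, the pooled rate is 0.0125/25 = 0.05%, W = 0.0001543/25 = 0.0000062, B = 0.0125² × 0.96/24 = 0.00000625 and T = 0.0000127. The interval is then roughly 0.05% ± 0.7%: no longer degenerate, but still crossing zero.

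**The case against.** The strongest reply is that these intervals decide nothing. Comparisons rest on the CMH test, the Mantel-Haenszel-Sato risk difference and the odds ratio. That stands. A reader might infer that a (0, 0) placebo interval distorts the formal evidence for early itch relief; the plan does not support that, because the comparison would be identical with any per-arm interval.

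A reader might also point to adolescents, at about four to six per arm, as the worst case. The plan specifies no per-arm interval for them. About 15 of 280 is 5.4%, and SAP Section 4.7.2.1 limits any group below 10% of the population to descriptive statistics. The only subgroup intervals it mentions are optional forest plots of treatment differences. Nor does the concern extend to Maintenance, where SAP Section 4.1.2.1 gives number and percentage only.

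The early rates are undocumented, and the large failures need true rates of about 2% or less at n = 80. That also stands. Low counts are nevertheless plausible: for participants with baseline IGA of at least 3, IGA 0 is a subset of the IGA 0/1 response, for which the placebo planning rate is only 13% even at Week 16.

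Finally, Section 4.1.1 never uses the word Wald, and the rate-and-SE recipe in Appendix 14 covers imputed data only. For NRI analyses Wald is the likelier reading, not an explicit statement. Naming the interval would settle this.

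**Conclusion.** The point holds as a minor reporting defect, confined to per-arm crude rates in the Induction Period. On the Wald reading, an NRI endpoint with no responders in an arm must print (0, 0); this needs no assumption about rates. An MCMC-MI endpoint does so only when all 25 data sets lack a responder, so it would be too strong to say that MI always has zero variance to combine.

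The loss of coverage is severe at true rates of 2% or less and moderate from 3% to 10%. Those rates are assumptions. The endpoints where they are plausible are IGA 0, SCORAD90, EASI-90, daily Itch response and weekly Itch response at Weeks 1 and 2. The co-primary results at the planned Week 16 rates are not affected in any way that matters.

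**What to change.** In SAP Section 4.1.1, name the Wilson score interval for per-arm crude proportions and apply it directly to NRI analyses.

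In SAP Appendix 14, replace the per-arm MI interval with an MI-adjusted Wilson interval. With pooled proportion p̄ and variance ratio r = (1 + 1/25)B/W, the limits are the two values of π that solve (p̄ − π)² = t²(1 + r)π(1 − π)/n, where t is the usual MI quantile. When no imputed data set has a responder, or all participants respond in all of them, r is 0/0. State that r is then set to 0, which gives the ordinary Wilson interval with the actual n (0 to 4.6% for 0/80). Without that sentence the adjusted form is undefined in the very case that prompts the change.

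Leave the Mantel-Haenszel-Sato interval, the CMH test, the odds ratio and the alpha allocation as they are. The cost is one PROC FREQ option for NRI, a short macro for MI, and intervals that are slightly asymmetric about the estimate.

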## 9.4. Statistical Analyses

### 9.4.1. General Considerations

Statistical analysis of this study will be the responsibility of the sponsor or its designee.

All tests of treatment effects will be conducted at a 2-sided alpha level of 0.05, unless otherwise stated, and all CIs will be given at a 2-sided 95% level.

For the efficacy and health outcome analyses during the Induction and Maintenance Periods, baseline is defined as the last available value before the first injection in the Induction Period. In most cases, this will be the value recorded at baseline visit (Visit 2, Week 0).

For safety analyses during the Induction Period, the Baseline Period is defined as the time from the screening visit (Visit 1) to the date/time of the first injection in the Induction Period. Baseline will be the last scheduled non-missing assessment recorded during the baseline period. Unless specified otherwise, for the safety analyses during the Maintenance Period, baseline is defined as the last available value before the first injection in the Maintenance Period. In most cases, this will be the measure recorded at Week 16.

Descriptive statistics will be used to provide an overview of the efficacy and safety results. For categorical parameters, the number and percentage of participants in each category will be presented. For continuous parameters, descriptive statistics will include number of participants (n), mean, SD, median, minimum, and maximum. Appropriate inferential statistics will be used for the primary and secondary efficacy variables.

The primary estimand that will be used to analyze primary and secondary endpoints is a composite variable strategy where comparisons will not include data collected after intercurrent events of changes to background therapies or discontinuation due to lack of efficacy (ICH E9 [R1]).

Any change to the data analysis methods described in the protocol will require an amendment only if it changes a principal feature of the protocol. Any other change to the data analysis methods described in the protocol, and the justification for making the change, will be described

in the statistical analysis plan (SAP) and the clinical study report. Additional exploratory analyses of the data will be conducted as deemed appropriate.

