#### **9.4.1.1. Missing Data Imputation**

The primary method of handling missing efficacy data after intercurrent events will be as discussed below for both binary and continuous endpoints.

For participants who receive rescue medication (high-/ultra-high-potency TCS or systemic AD treatment) or withdraw from the study due to lack of efficacy, the participant's baseline value will be carried forward to the subsequent time points through Week 16. Markov Chain Monte Carlo multiple imputation will be used to handle the remaining missing data.

Sensitivity analyses will be addressed in the SAP.

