#### **9.4.3.2. Secondary Analyses**

For secondary binary efficacy and health outcome endpoints during the Induction Period, the CMH test will be used to compare the treatment groups while adjusting for the stratification factors (disease severity: IGA 3 versus 4, and age: adolescent participants  $\geq 12$  to  $< 18$  years versus  $\geq 18$  years).

Treatment comparisons of secondary continuous efficacy and health outcome endpoints during the Induction Period will be made using an analysis of covariance with the following in the model: treatment group, baseline value, and stratification factors.

Efficacy, health outcome, and safety measures during the Maintenance Period will be summarized using descriptive statistics by treatment group.

More details will be specified in the SAP.

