##### Supplemental analyses

Supplemental analyses will be performed on the co-primary endpoints using another composite variable strategy where comparisons will not include data collected after intercurrent events of changes to background therapies or discontinuation due to lack of efficacy ([ICH E9 [R1] Step 4 2019]). For participants who receive rescue medication, their values while on rescue medication will be set to missing.

Analysis details will be described in the SAP.

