4.1.6.1.4. Mixed-effects Model for Repeated Measures (MMRM)

Mixed-effects model for repeated measures analyses will be performed on continuous endpoints to mitigate the impact of missing data. This approach assumes missing observations are missing-at-random (missingness is related to observed data) and borrows information from participants in the same treatment arm taking into account both the missingness of data through the correlation of the repeated measurements.

The values subsequent to rescue medication use (i.e., high-potency TCS or systemic AD treatment, defined in [Appendix 13](#)) or treatment discontinuation will be made missing before applying the MMRM model. The MMRM model is described in Section [4.1.1](#).

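### Change scores for eight secondary instruments in the Induction Period move from the protocol's composite ANCOVA to a hypothetical-estimand MMRM, the protocol's supplemental co-primary analysis is not carried over, and SAP 4.9 records neither departure

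*SAP*

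**What the plan says.** **Protocol.** Section 9.4.1 sets a single estimand: "The primary estimand that will be used to analyze primary and secondary endpoints is a composite variable strategy". Section 9.4.1.1 applies its rule to binary and continuous endpoints alike. After rescue, or withdrawal for lack of efficacy, the participant's "baseline value will be carried forward to the subsequent time points through Week 16", and MCMC multiple imputation covers whatever else is missing. Section 9.4.3.2 names the model: "Treatment comparisons of secondary continuous efficacy and health outcome endpoints during the Induction Period will be made using an analysis of covariance", with treatment, baseline value and stratification factors. Section 9.4.7 adds a supplemental analysis of the co-primary endpoints: "For participants who receive rescue medication, their values while on rescue medication will be set to missing".

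**SAP.** The imputation table in 4.1.6.1 keeps the primary (hybrid) estimand for IGA, EASI and Itch NRS. Remaining continuous endpoints measured repeatedly are assigned the supportive hypothetical estimand only, analysed as in 4.1.1: "Treatment comparisons of other continuous efficacy variables and health outcome variables with multiple post-baseline measurements will be made using mixed-model for repeated measures (MMRM"). Under 4.1.6.1.4, values after rescue or "treatment discontinuation will be made missing before applying the MMRM model". For the co-primary endpoints, 4.3.3 and 4.3.4 plan a tipping point analysis, an NRI analysis under the composite supportive estimand, and a repeat on the PPS.

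**Record of changes.** SAP 4.9 has two entries: removal of the Skin Pain-free days analysis, and "Updated definition of analysis population for the Maintenance Period".

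**The concern.** The two documents assign the same endpoints to different clinical questions. The protocol asks how far participants improve when needing rescue, or leaving for lack of efficacy, counts as no improvement. The SAP asks how far they would have improved had rescue not existed and everyone stayed on treatment. For EASI and Itch NRS the SAP keeps the protocol's question as the main analysis and makes the MMRM supplementary. For the eight other instruments the MMRM is the only analysis of change, so change scores in one report would not be comparable across instruments.

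The supplemental analysis matters for a separate reason. It is the one place where the protocol would vary how rescue is handled for EASI-75 and IGA 0/1. Without it, no planned analysis shows how far the co-primary result depends on counting rescue as failure.

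Protocol 9.4.1 says that non-principal changes to the analysis methods, with their justification, will be described in the SAP and in the clinical study report. SAP 4.1 promises this in the clinical study report only. A reader who takes 4.9 as complete would not learn that either change was made.

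**Working it through.** **1. The plan's own figure.** The only reproducible figure nearby is the power statement (protocol 9.2, SAP 5). Inputs are 120/80/80 participants, IGA 0/1 rates of 38%, 33% and 13%, EASI-75 rates of 58%, 53% and 20%, and a two-sided Fisher exact test at 0.05. Exact enumeration gives:
- Q2W: 98.0% for IGA 0/1 and above 99.9% for EASI-75. The lower bound for both together is 0.9795 + 0.9998 − 1 = 97.9%.
- Q4W: 82.5% and 99.1%. The lower bound is 0.8254 + 0.9906 − 1 = 81.6%.

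The stated >95% and >80% hold, and nothing in this point alters them.

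**2. The endpoints, side by side (Induction Period).**

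| Endpoint | Protocol 9.4.1, 9.4.1.1, 9.4.3.2 | SAP 4.1.6.1 and Appendix 2 |
|---|---|---|
| EASI and Itch NRS change | Baseline value after event, MCMC-MI, ANCOVA | Same; MMRM supplementary |
| BSA, Skin Pain, Sleep-loss, DLQI/CDLQI, SCORAD, POEM, WPAI-AD and HADS change | Same rule | Hypothetical estimand, MMRM only |
| ACQ-5 change | Same rule | Hypothetical estimand, ANCOVA with LOCF |
| TCS amount, TCS/TCI-free days | Not singled out | t-test and ANOVA on observed data |

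The MMRM switch is the second row. Neither rule uses measurements taken after rescue. They differ in what stands in for them: the baseline value, or a model-based prediction under missing at random.

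**3. The co-primary analyses.** In the SAP, rescue leads to the baseline value (main analysis and PPS repeat) or to non-response (NRI and tipping point). SAP 4.1.6.1.2 varies only the other missing data. Protocol 9.4.7 would blank the values recorded while on rescue, and no SAP analysis does that.

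**4. Illustration of size. All inputs are assumed; none is in the documents.** Let dL and dP be the mean changes in participants without an event, rL and rP the event shares, and f the fraction of that mean change which the model predicts for participants with an event.
- Composite difference = (1 − rL)dL − (1 − rP)dP
- Hypothetical difference = dL(1 − rL + f·rL) − dP(1 − rP + f·rP)

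Take DLQI changes dL = −9 and dP = −5.

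| rL / rP | Composite | Hypothetical, f = 1 | Hypothetical, f = 0.5 |
|---|---|---|---|
| 3% / 10% | −8.73 + 4.50 = −4.23 | −4.00 | −4.12 |
| 5% / 20% | −8.55 + 4.00 = −4.55 | −4.00 | −4.28 |
| 10% / 30% | −8.10 + 3.50 = −4.60 | −4.00 | −4.30 |

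Relative to the hypothetical difference, the composite one is 6% to 15% larger at f = 1 and 3% to 7% larger at f = 0.5. The placebo mean change is larger under the hypothetical rule by 11% to 43% (f = 1) or 6% to 21% (f = 0.5). The direction depends on the inputs: the composite difference is the larger only while 5·rP exceeds 9·rL, that is, while the placebo event share is more than 1.8 times the active one.

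**5. The same illustration for EASI-75.** Assume response of 58% (Q2W) and 20% (placebo) among participants not rescued. With rescue as failure, the differences are 0.98 × 58 − 0.90 × 20 = 38.8 points (rescue 2%/10%), 39.1 (5%/20%) and 38.2 (10%/30%). If rescued participants are imputed at their arm's rate, the difference is 38.0.

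**The case against.** **Scope of the protocol commitment.** Section 9.4.1 describes section 9 as a summary of the most important endpoints and leaves technical detail to the SAP. The co-primary and major secondary endpoints keep the protocol's handling, and the affected endpoints lie outside the testing scheme. This limits the importance of the point, but 9.4.3.2 names secondary continuous efficacy and health outcome endpoints explicitly, so the contradiction stands.

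**Rescue is not ignored for every instrument.** A reader might infer that quality of life and SCORAD would be reported as though rescue were never needed. Appendix 2 does not support that. It has NRI responder analyses, with rescue as non-response, for DLQI/CDLQI (4-point improvement and 0/1), SCORAD75/90, Skin Pain (4-point) and Sleep-loss (2-point). Only BSA, POEM, WPAI-AD and HADS have no composite counterpart.

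**The supplemental analysis is ambiguous.** Protocol 9.4.7 calls its strategy composite, does not say how the missing values are to be filled, and defers details to the SAP. If missing counts as non-response, the SAP's NRI is nearly the same for rescued participants. So the protocol cannot be said to have clearly promised a test of the rescue-as-failure rule. What stands is that the stated step is absent and the SAP does not say how it was interpreted.

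**No bias towards the drug.** A reader might infer that the SAP's choice flatters lebrikizumab. The documents do not show this, and the illustration gives a smaller difference under the SAP's rule. A larger placebo change under a hypothetical estimand answers a different question; it is not an error. The f = 1 column is also near an upper bound, because an MMRM uses rescued participants' own pre-rescue values.

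**Transparency.** The methods are openly stated in the SAP, and intercurrent events will be summarised by arm. That is fair, but stating a method does not identify or justify it as a change.

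**Conclusion.** The point holds as a contradiction between protocol and SAP, and as an incomplete record of changes. It covers change from baseline in eight instruments during the Induction Period, plus one supplemental analysis of the two co-primary endpoints. It is not a finding of bias, and it does not touch power, alpha control, or the main analyses of the co-primary and major secondary endpoints.

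The size cannot be derived from the documents, which give neither expected rescue rates nor expected change scores. Under the assumptions shown, the DLQI treatment difference differs by about 3% to 15% between the two rules, and the EASI-75 difference by about 0.2 to 1.1 percentage points. Those ranges show only that the estimands can separate when rescue differs between arms. The case for a change rests on fidelity to the protocol and comparability across endpoints.

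**What to change.** 1. **SAP Appendix 2 and the table in 4.1.6.1:** for change in BSA, Skin Pain NRS, Sleep-loss, DLQI, SCORAD, POEM, WPAI-AD and HADS, add the protocol's analysis at Week 16 (set to baseline, MCMC-MI, ANCOVA), at least as a supplementary analysis. Making it the main analysis is a matter of judgement and is not needed to close the gap. CDLQI may be excepted: about 15 adolescents at 3:2:2 puts about 15 × 2/7 ≈ 4 on placebo, and only those aged 16 or under complete it, which is too few for imputation within arm.
2. **SAP 4.3.4:** add the protocol 9.4.7 analysis for EASI-75 and IGA 0/1 as supplementary, with values on rescue set to missing and then multiply imputed. State that this is how the protocol's wording is read.
3. **SAP 4.9:** list and justify any departure that is kept, including the move to MMRM under the hypothetical estimand if it remains the main analysis. Align SAP 4.1 with protocol 9.4.1 on where changes are described.

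The cost is SAP wording, a little extra programming that can start from the existing EASI and Itch NRS imputation, and a few more tables. No new data are needed.
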